### 10.3 Deaths, Serious Adverse Events and other Significant Adverse Events

The summary statistics will be produced in accordance with section 8.

## 11 Figures

The figures that will be produced include, but are not limited to:

Box plots:

- Peanut threshold at baseline and end of phase 1 (and phase 2 for waiting list group) by group
- Serum peanut specific IgE (log) at baseline and end of phase 1 (and phase 2 for waiting list group) by group
- SPT at baseline and end of phase 1 (and phase 2 for waiting list group) by group

Plot of basophil histamine release CD63MFI and %CD63 positive cells against peanut protein concentration (baseline and phase 1 (and phase 2 for waiting list group)) by group

Plot of probability of desensitisation to peanut according to logistic regression model with a continuous independent covariate on the x-axis (possibly baseline peanut IgE, threshold or age), separate lines for treatment groups and appropriate constants chosen for all other covariates.

Plot of probability of response to treatment to peanut according to logistic regression model with a continuous independent covariate on the x-axis (possibly baseline peanut IgE, threshold, or age), separate lines for treatment groups and appropriate constants chosen for all other covariates.

## 12 Reporting Conventions

P-values  $\geq 0.001$  will be reported to 3 decimal places; p-values less than 0.001 will be reported as “<0.001”. The mean, standard deviation, and any other statistics other than quantiles, will be reported to one decimal place greater than the original data. Quantiles, such as median, or minimum and maximum will use the same number of decimal places as the original data. Estimated parameters, not on the same scale as raw observations (e.g. regression coefficients) will be reported to 3 significant figures.

## 13 Listing of Tables and Figures

A summary of the tables and figures to be included in the final report are given in the tables in this section

### 13.1 Tables

Table Title	No.	Population	Endpoint	Time Points or how to conglomerate	Covariates or Subgroups	Summary Statistics	Formal Analysis
Summary of patient characteristics	1.1	Full analysis	Age	Baseline	Treatment	n, mean, SD	NA
			Sex			n, %	
			Weight			n, mean, SD	
			Asthma			n, %	
			Eczema			n, %	
			Rhinitis			n, %	
			Other food allergy			n, %	
			Tryptase			n, mean, SD	
			WAO score (historical)			n, median, range	
			Sensitisation to tree nuts			n, %	
			QoL score			n, median, range	
			Peanut specific IgE			n, median, range	
			Total IgE			n, median, range	
			Peanut SPT wheal diameter			n, mean, SD	
			Other nut SPT wheal diameter			n, mean, SD	
			Family history of peanut allergy			n, %	
			DBPCFC total peanut protein consumed			n, median, range	
DBPCFC peanut threshold (NOEL)	n, mean, SD						
DBPCFC WAO score	n, median, range						
DBPCFC LOAEL	n, mean, SD						

Basophil AUC of CD63MFI  
against peanut protein  
concentration

n, mean , SD

Basophil AUC of %CD63 positive  
cells against peanut protein  
concentration

n, mean, SD

Desensitisation to peanut after 6 months	2.1	Full analysis	Allergy desensitised or undesensitised	6 months	Treatment	n, %, odds ratio, 95% CI	Fishers exact test
					Treatment		
					Age		
					Sex		
					Asthma		
					Eczema		
					Rhinitis		
					Weight		
Logistic regression - adjusted odds of desensitised peanut allergy	2.2	Full analysis	Allergy desensitised or undesensitised	6 months	Sensitisation to tree nuts	odds ratios, 95% CI	Logistic regression
					Peanut specific IgE		
					Peanut SPT wheal diameter		
					Basophil AUC of CD63MFI against peanut protein concentration		
					QoL score		
					Family history of allergy		
					Baseline NOAEL		
Comparison of change in threshold between treatment groups	2.3	Full analysis	Threshold	Baseline and 6 months	Treatment	mean, SD, absolute and fold difference, 95% CI	t-test

Comparison of change in quality of life score between treatment groups	2.4	Full analysis	Quality of life score	Baseline and 6 months	Treatment	median, range, difference, 95% CI	Mann-Whitney U test
Comparison of change in quality of life score before and after intervention within and between treatment groups	2.5	Full analysis	Quality of life score	Baseline and 6 months (immunotherapy) 6 and 12 months (Waiting list)	Treatment	median, range, difference, 95% CI	Wilcoxon sign rank test Mann-Whitney U test
Comparison of change in peanut immunological outcomes between treatment groups	2.6	Full analysis	Peanut IgE Total IgE Peanut SPT Other nut SPT Basophil histamine release CD63MFI (AUC) Basophil histamine release %CD63 positive cells (AUC)	Baseline and 6 months	Treatment	median, range, difference, 95% CI	Mann-Whitney U tests
Comparison of change in WAO score between treatment groups	2.7	Full analysis	WAO score	Baseline and 6 months	Treatment	median, range, difference, 95% CI	Mann-Whitney U tests
Predictors of treatment response	2.8	All patients who underwent immunotherapy	Response to immunotherapy	6 months (or 12 months for Waiting list group)	Treatment Age Sex Asthma Eczema Rhinitis Weight	odds ratios, 95% CI	Logistic regression

Sensitisation to tree nuts

Peanut specific IgE

Peanut SPT wheal diameter

Basophil AUC of CD63MFI against peanut protein concentration

QoL score

Family history of allergy peanut

Baseline NOAEL

Adverse events per dose	2.9	Safety population	Mouth itching Abdominal pain Nausea Vomiting Diarrhoea Urticaria Angioedema Erythema Rhinitis Wheezing Laryngeal oedema Cardiovascular collapse Fainting Admission to ITU Serious adverse reaction SUSAR	End of study	Treatment	n, %	NA
-------------------------	-----	-------------------	---	--------------	-----------	------	----

Use of nebulised beta 2 agonist

Use of intramuscular adrenaline

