## 5 Study Methods

### 5.1 General Study Design and Plan

Single centre, randomized controlled trial of a novel active intervention (peanut oral immunotherapy) versus the status quo (peanut avoidance) in patients with peanut allergy. Two phase (package) design.

- Phase 1: Subjects randomly allocated (using minimisation methods – 80% chance of being assigned to imbalance minimising arm) to active intervention arm or waiting list arm. After 6 months all patients will be assessed for peanut allergy.
- Phase 2: Participants in waiting list arm still allergic to peanut at the end of phase 1 will be given the active intervention.

The figure below shows the study design.

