### 5.4 Study Variables

The visit schedule is shown below:

Week	0	Phase 1										Phase 2									
		2	4	6	8	10	12	14	16	18	24	26*	28*	30*	32*	34*	36*	38*	40*	42*	48*
Active immunotherapy visit	1	2	3	4	5	6	7	8	9	10	11	-	-	-	-	-	-	-	-	-	-
Waiting list visit*	(Baseline)	-	-	-	-	-	-	-	-	-	2	3*	4*	5*	6*	7*	8*	9*	10*	11*	12*
Demographics	x																				
Other allergies	x																				
WAO score (historical)	x																				
DBPCFC (NOAEL, LOAEL, WAO score)	x									x											x
Peanut SPT	x									x											x
Other nut SPT	x									x											x
Peanut specific IgE	x									x											x
Total IgE	x									x											x
Basophil histamine release	x									x											x
Tryptase	x																				
QoL questionnaire	x									x											x
OIT updose*		x	x	x	x	x	x	x	x	x	x	x	x	x	x	x	x	x	x	x	x

*\*Only waiting list patients who are not desensitised to peanut after 24 weeks undergo immunotherapy from week 26 to 48*

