## 6 Sample Size

Based on Fisher's exact test with 90% power and 5% significance (two-sided) a sample size of 49 in each group is sufficient to detect proportions of participants with desensitisation to peanut of 64% and 30% in the intervention and control group respectively. Allowing for 5% drop out increases the sample size to 52 participants in each group and 104 subjects overall.

Based on the above we would expect 35 waiting list group patients to proceed to the active intervention in phase 2. To confirm efficacy of immunotherapy the success rate of all participants (intervention and phase 2 waiting list) should be within 10% of the success rate seen in intervention participants alone in phase 1.

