## 7.2 Covariates and Subgroups

The covariates that are recorded at baseline are:

- Demographics (age, sex, weight, family history of allergy)
- Other allergic diseases (asthma, eczema, rhinitis)
- Sensitisation to tree nuts
- Severity of worst reaction before enrolment (WAO score)
- DBPCFC – WAO score, LOAEL, NOAEL
- Peanut SPT wheal diameter
- Other nut SPT wheal diameter
- Peanut specific IgE
- Total IgE
- Basophil AUC of CD63MFI against peanut protein concentration
- Basophil AUC of %CD63 positive cells against peanut protein concentration
- Tryptase
- QoL score

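### Table 2.8 takes the waiting-list outcome at 12 months but leaves five re-measured predictors at week 0, about six months before that group starts immunotherapy

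*SAP*

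**What the plan says.** **Population and outcome.** In SAP Section 13.1, Table 2.8 (predictors of treatment response) has the population "All patients who underwent immunotherapy". This pools the intervention arm with the waiting-list participants treated in phase 2. Response is taken at "6 months (or 12 months for Waiting list group".

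**Covariates.** Table 2.8 lists 14 terms: treatment, age, sex, asthma, eczema, rhinitis, weight, tree-nut sensitisation, peanut IgE, peanut SPT, basophil AUC, QoL, family history and "Baseline NOAEL". Section 9.2 says the logistic model for response adjusts for the characteristics in Section 7.2. That list opens with "The covariates that are recorded at baseline are".

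**Meaning of baseline.** The schedule in Section 5.4 attaches the word to week 0 for both arms. Figures 2.1 to 2.5 in Section 13.2 list baseline as a separate time point from the end of phase 1.

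**Start of treatment.** The note under the schedule reads "Only waiting list patients who are not desensitised to peanut after 24 weeks undergo immunotherapy from week 26 to 48". Section 5.1 adds "After 6 months all patients will be assessed for peanut allergy".

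**The parallel case.** For QoL before and after treatment, Section 9.2 and Table 2.5 take the waiting-list change from 6 to 12 months. There the end of phase 1 is the pre-treatment value. Table 2.8 has no corresponding rule.

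**The concern.** The outcome clock is moved for the waiting-list group but the predictor clock is not. In the intervention arm, week 0 is both enrolment and the start of treatment. In the waiting-list group the two are about six months apart. A pooled coefficient for a changing marker therefore mixes two relations: response on a current value in one group, and response on a superseded value in the other.

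The treatment term can absorb an average shift between week 0 and the end of phase 1. It cannot absorb individual participants changing rank. The SAP's own definitions leave room for this. Entry to phase 2 requires only failing to reach 1400 mg, while response means tolerating 800 mg (Section 4.3). A participant whose threshold had drifted to between those figures by the end of phase 1 would enter treatment already at the response level, yet would be modelled on a lower week 0 threshold.

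At stake is the interpretation of a secondary table. Markers that do predict response could look weaker than they are. In addition, with two eligible readings of each marker and no explicit rule, the choice could be made after the results are seen.

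**Working it through.** **1. The SAP's own figures.** Section 6 states "Based on Fisher's exact test with 90% power and 5% significance (two-sided) a sample size of 49 in each group" for rates of 64% and 30%.
- Exact Fisher power is 0.906 at 49 per arm and 0.896 at 48, so 49 is reproduced.
- Drop-out: 49 / 0.95 = 51.6, rounded up to 52.
- Waiting-list participants treated: 0.70 × 49 = 34.3, or 0.70 × 0.95 × 52 = 34.6. Either rounds up to the 35 in "Based on the above we would expect 35 waiting list group patients to proceed to the active intervention in phase 2".

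**2. Share of participants affected.** 35 / (35 + 52) = 40.2%, or 35 / (35 + 49) = 41.7% on evaluable numbers.

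**3. Which predictors are affected.**
- Five of the 14 terms vary over time and are measured again before phase 2: NOAEL, peanut SPT, peanut IgE, basophil AUC and QoL. The schedule shows a second assessment of each. Section 9.2 also needs end-of-phase-1 values in both groups for its between-group comparisons. The column position of that assessment in the available text of the schedule is unreliable, so the 6 months of Section 5.1 is used here.
- Sex and family history do not go out of date, and age moves by a near-constant. Demographics and other allergies are scheduled at week 0 only.
- Share of all predictor values affected: 40.2% × 5/14 = 14.4%, or 41.7% × 5/14 = 14.9%. Counting tree-nut sensitisation (through other-nut SPT) gives 17–18%. Adding weight gives 20–21%.

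**4. Size of the attenuation.** Assumptions, none of them in the SAP:
- response depends on the standardised value at treatment start;
- the week 0 value in the waiting-list group correlates ρ with it, with equal variance;
- the other group's values are exact, and the model has a group term.

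A first approximation to the fraction of the log odds ratio retained is (52 + 35ρ) / 87. At ρ = 0.8 this is 80 / 87 = 0.920. The next columns come from large simulated logistic models (435,000 subjects, intercept 1.0, 35/87 in the waiting-list group).

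| ρ | (52 + 35ρ)/87 | Simulated, true OR 1.65 | Simulated, true OR 2.72 | OR 2.72 becomes |
|---|---|---|---|---|
| 0.95 | 0.980 | 0.980 | 0.976 | 2.65 |
| 0.9 | 0.960 | 0.944 | 0.941 | 2.56 |
| 0.8 | 0.920 | 0.902 | 0.893 | 2.44 |
| 0.7 | 0.879 | 0.875 | 0.840 | 2.32 |
| 0.5 | 0.799 | 0.783 | 0.749 | 2.11 |

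At ρ = 1 the simulation returned 1.014 and 0.999 instead of 1, so the OR 1.65 column is good to about one or two percentage points.

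A separate simulation with a true OR of 0.50 gave 0.51, 0.53, 0.57 and 0.59 at ρ = 0.95, 0.8, 0.6 and 0.5. As fractions retained: ln 0.51 / ln 0.50 = 0.97, ln 0.53 / ln 0.50 = 0.92, ln 0.57 / ln 0.50 = 0.81 and ln 0.59 / ln 0.50 = 0.76. The two sets agree.

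**The case against.** The strongest case against has four parts.

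**The text is not explicit.** Only NOAEL carries the word baseline in Table 2.8; the other terms have no time label. That is true. But Sections 5.4, 7.2, 9.2 and 13.2 together leave week 0 as the natural reading, and an analyst following them would use it.

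**Week 0 need not be the worse reading.** If response depends on a stable trait, both measurements are noisy versions of it and neither has a clear advantage. Prediction from features at enrolment is also a legitimate question. This stands in part: it is why the attenuation is conditional and why week 0 values should be kept as a sensitivity analysis. It does not rescue the pooled model as the main one, because the interval from enrolment to treatment differs by about six months between the groups.

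**The loss may be small.** At a correlation of 0.9 or more it is about 6% or less on the log-odds scale. This stands.

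**Threshold drift is not shown.** A reader might take the assumed 30% desensitisation among controls as proof that thresholds move. Those participants do not enter phase 2 and so are not in Table 2.8. The 30% says nothing direct about the 35 or so who remain. Because entry is selected on the week 24 challenge, the direction of any bias for NOAEL is itself less certain.

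**Conclusion.** The point holds as a mismatch of timing within one secondary model. Followed as written, five of the 14 terms in Table 2.8 would be about six months out of date for roughly 40% of participants, although newer values are collected and Table 2.5 already uses the newer one for QoL.

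If the value at treatment start is the relevant predictor, the odds ratios for these five are likely pulled toward 1. The loss on the log-odds scale is about 2–3% at a correlation of 0.95, about 10% at 0.8 and about 25% at 0.5. The correlation is an assumption, the model is simple, and the simulation does not include selection into phase 2.

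Three stronger readings are not supported:
- That about 40% of all predictor values are out of date. The 40% applies to participants within each affected covariate; across all 14 terms it is about 14–15%.
- That dilution is established. Its size rests on a correlation the SAP does not give, and its direction for NOAEL is open.
- That Figure 2.7 shares the fault. Its stated population is the full analysis set, so it cannot be assumed to plot the Table 2.8 model.

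The primary comparison and the sample size are not touched.

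**What to change.** In Table 2.8, define NOAEL, peanut SPT, peanut IgE, basophil AUC and QoL as the last value before the first immunotherapy dose: week 0 for the intervention group, the end-of-phase-1 assessment for the waiting-list group. Rename "Baseline NOAEL" in that table to *pre-immunotherapy NOAEL*. Keep week 0 values for covariates that are not re-measured. Repeat the model with week 0 values throughout as a sensitivity analysis. Apply the same definition to Figure 2.7 only if that figure plots the Table 2.8 model, and say whether it does.

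The cost is a few lines of SAP wording and one extra model run. The schedule already collects all five at the end of phase 1, so no new data are needed. The rule should be fixed before the response data are analysed.

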## 13.2 Figures

Title	No.	Population	Type of graph	Horizontal Variables	Vertical Variables	Groupings
CONSORT diagram	1.1		Flow chart			
Peanut Threshold	2.1	Full analysis	Box plot	Peanut threshold (NOAEL) (mg)	NA	Treatment and time (Baseline, end of phase 1 and end of phase 2)
Peanut IgE	2.2	Full analysis	Box plot	Peanut IgE (kU/L); log	NA	Treatment and time (Baseline, end of phase 1 and end of phase 2)
Skin Prick Test	2.3	Full analysis	Box plot	Peanut SPT diameter (mm)	NA	Treatment and time (Baseline end of phase 1 and end of phase 2)
Basophil histamine release	2.4	Full analysis	Line	Peanut concentration	mean fluorescent intensity of CD63	Treatment and time (Baseline, end of phase 1 and end of phase 2)
Basophil histamine release	2.5	Full analysis	Line	Peanut concentration	%CD63 positive cells	Treatment and time (Baseline, end of phase 1 and end of phase 2)
Probability of desensitisation	2.6	Full analysis	Line	Baseline NOAEL	Probability	Treatment
Probability of treatment response	2.7	Full analysis	Line	Baseline NOAEL	Probability	Treatment
